4.2.5. Protocol Deviations

Protocol deviations (PDs) will be regularly reviewed by Vir, particularly before database cutoff dates for IAs. A final review of PDs will be conducted prior to the study database lock. Any PDs identified after the database lock will be included in the analyses and identified as such in the CSR.

An important PD is a PD that may significantly impact the completeness, accuracy, and/or reliability of study data or that may significantly affect a participant's rights, safety, or well-being.

A by-participant listing of all important PDs and COVID-19 related PDs will be provided with columns identifying the date of the deviation, deviation category, and the verbatim description of the deviation.

4.3. Primary Endpoint Analysis

The primary efficacy endpoint analyses will be based on the FAS.

4.3.1. Primary Endpoint

The primary efficacy endpoint is the proportion of participants achieving suppression of HBV DNA (< LLOQ) with HBsAg loss (< 0.05 IU/mL) at EOT. The LLOQ for HBV DNA is 20 IU/mL.

The number and proportion of participants achieving the combined response variable – the suppression of HBV DNA (< LLOQ) with HBsAg loss (< 0.05 IU/mL) – at EOT will be summarized, and the two-sided 95% exact Clopper-Pearson confidence interval (CI) will be calculated for each cohort.

If a participant misses HBV DNA or HBsAg at EOT, then this participant will be considered not meeting the primary endpoint.

HBV DNA and HBsAg values will be provided in a by-participant listing.

4.3.2. Supplementary Analysis

Two supplementary analyses will be performed for the primary efficacy analysis.

For the first supplementary analysis, the number and percentage of the participants meeting the primary efficacy endpoint – achieving suppression of HBV DNA (< LLOQ) with HBsAg loss (< 0.05 IU/mL) at EOT – will be summarized based on the FAS excluding those participants who have prematurely discontinued all interventions during the Treatment Period before the planned EOT.

For the second supplementary analysis, the number and percentage of the participants meeting the primary efficacy endpoint – achieving suppression of HBV DNA (< LLOQ) with HBsAg loss (< 0.05 IU/mL) at EOT – will be summarized based on the FAS excluding those participants who have missed or discontinued any dose of study intervention before the planned EOT.

The two-sided 95% exact Clopper-Pearson CI by cohort will also be calculated for each supplementary analysis.

4.3.3. Subgroup Analysis

Not applicable.

4.4. Secondary Endpoints Analysis

4.4.1. Secondary Efficacy Endpoints

The analysis of the following secondary endpoints will be conducted based on the FAS, unless otherwise specified. The numbering in the table below is consistent with the numbering of the endpoints in [Table 1](#). HBeAg, anti-HBsAg, and anti-HBeAg values will be provided in a by-participant listing.

Secondary Endpoints	Analysis Methods

 2. Proportion of participants with serum HBsAg ≤ 10 IU/mL at the EOT 3. Proportion of participants with serum HBsAg ≤ 10 IU/mL at 24 weeks post-EOT 8. Proportion of participants with HBsAg loss with anti-HBs seroconversion at EOT and at 24 weeks post-EOT 10. Proportion of participants achieving HBsAg loss (< 0.05 IU/mL) 
 a. at EOT b. at 24 weeks post-EOT 	
The number and proportion of participants for each endpoint will be summarized at each visit by cohort, and the two-sided 95% Clopper-Pearson CI will be calculated for each cohort.

 4. Serum HBsAg levels and change from baseline across timepoints in the study 5. Serum HBsAg level at nadir during the study 14. Mean change in serum HBsAg level from baseline across timepoints in the study 	
The observed values and the absolute change from baseline values in both IU/mL and \log_{10} IU/mL of HBsAg
 
at each visit up to end of study (EOS)
 
at nadir during the study
 
will be summarized using descriptive statistics (n, mean, SD, median, Q1, Q3, min, max) by cohort.
 
In addition, the change from baseline in \log_{10} IU/mL at each visit will be plotted for each participant by cohort.
 
Absolute value in \log_{10} IU/mL at each visit will be plotted for each participant by cohort.
 
Mean change from baseline in \log_{10} IU/mL at each visit will be plotted for each cohort.

6. Time to achieve nadir of serum HBsAg during the study
 
7. Time to achieve serum HBsAg loss (< 0.05 IU/mL)
	
Time-to-nadir of serum HBsAg during the study period (up to EOS) will be summarized as a continuous variable by cohort.
 
Time-to-HBsAg loss will be summarized as a continuous variable by cohort.


9. Proportion of participants achieving sustained suppression of HBV DNA (< LLOQ) with HBsAg loss (< 0.05 IU/mL) after discontinuation of all treatment:
 
a. at 24 weeks
 
b. at the F48 Follow-Up visit
 
11. Proportion of participants achieving sustained suppression of HBV DNA (< LLOQ) after discontinuation of all treatment:
 
a. at 24 weeks
 
b. at the F48 Follow-Up visit
	
Due to early study termination, modification to timepoints of a. and b. as below:
 
a) at 24 weeks after discontinuation of all treatments (an analysis window of 168 ± 14 days will be applied to capture data around the 24 weeks timepoint, following the rules in Appendix 2 for data selection)
 
b) at the last Follow-Up visit, for participants who have > 24 weeks of discontinuation, after discontinuation of all treatments
 
c) at the last Follow-Up visit after discontinuation of all treatments (all participants will be included in the denominator)
 
Specifically, for a) and b), the denominator used in the percentage calculation will exclude participants with uncertain NRTI discontinuation status due to early study termination (e.g., no Follow-Up 12 visit).
 
The number and percentage of participants achieving
 
 • sustained suppression of HBV DNA (< LLOQ) • sustained suppression of HBV DNA (< LLOQ) with HBsAg loss (< 0.05 IU/mL) 
will be summarized by cohort with the two-sided 95% Clopper-Pearson CI.
 
In addition, the number and percentage of participants achieving
 
 • sustained suppression of HBV DNA (< LLOQ), allowing transient viremia

	
 • sustained suppression of HBV DNA (< LLOQ) with HBsAg loss (< 0.05 IU/mL), allowing transient viremia where transient viremia is defined as HBV DNA \geq LLOQ or HBsAg \geq LLOQ for \leq 35 days, adapted from the 2022 American Association for the Study of Liver Diseases (AASLD) – The European Association for the Study of the Liver (EASL) functional cure definition (AASLD-EASL, 2022), will be analyzed similarly. 
Similarly, the analyses above will be repeated after replacing “HBsAg loss (<0.05 IU/mL) with “HBsAg < 100 IU/mL”. Accordingly, the transient viremia is defined as HBV DNA \geq LLOQ or HBsAg \geq 100 IU/mL for \leq 35 days, adapted from the 2022 AASLD-EASL partial functional cure definition (AASLD-EASL, 2022).

12. For HBeAg-positive participants: proportion of participants with HBeAg loss (undetectable HBeAg) and/or anti-HBe seroconversion	
The number and percentage of participants achieving
 
 • HBeAg loss (undetectable HBeAg) will be summarized at each visit up to EOS by cohort for each visit; and • Anti-HBe seroconversion • HBeAg loss (undetectable HBeAg) and anti-HBe seroconversion will be summarized at each follow-up visit by cohort up to EOS. The two-sided 95% Clopper-Pearson CI will also be calculated at each follow-up visit for each cohort. 
The percentage will be based on those participants who have HBeAg tested positive at baseline in the FAS.

15. Proportion of participants achieving HBV DNA < LLOQ across timepoints in the study	
The number and percentage of participants with
 
 • HBV DNA < LLOQ • ALT \leq ULN

16. Proportion of participants achieving ALT \leq ULN across timepoints in the study	
will be summarized at each visit by cohort. The two-sided 95% Clopper-Pearson CI will also be calculated across visits for each cohort.
 
In addition, the individual ALT (U/L) value at each visit will be plotted for each participant by cohort.

--	---

- The LLOQ for HBV DNA is 20 IU/mL.
- HBsAg loss is defined as HBsAg < 0.05 IU/mL.
- Anti-HBs seroconversion: Anti-HBs change from baseline negative to post-baseline positive. The quantitative results will be used. The definition of negative, indeterminate, and positive is < 8.50 mIU/mL, ≥ 8.50 mIU/mL and < 11.50 mIU/mL, and ≥ 11.50 mIU/mL, respectively. If a result is “indeterminate”, a further assessment or judgement will be performed to determine positive or negative.
- HBeAg-positive participants: the qualitative results at Screening will be used to determine if a participant is HBeAg-positive. In case a participant has a missing qualitative result in screening, the most recent non-missing qualitative result before the first dose of the study intervention will be used. If the qualitative result is not available, then the most recent non-missing quantitative value before the first dose of the study intervention will be used.
- Undetectable HBeAg/HBeAg loss: HBeAg < 0.06 IU/mL.
- Anti-HBe seroconversion: Anti-HBe changes from baseline negative to post-baseline positive. Anti-HBe qualitative data at Screening will be used for baseline assessment. Anti-HBe qualitative data collected during the Follow-Up Period will be used for post-baseline assessment.
- Nadir of HBsAg (or HBV DNA): Nadir is defined as the lowest HBsAg (or HBV DNA) value among all scheduled and unscheduled post-baseline HBsAg (or HBV DNA) values.

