1.2.3. Intervention Groups and Duration

There are 5 cohorts planned in this sub-study.

Table 3: Intervention Groups

Cohort	Study Drug	Dose	Route	Number of Doses	Frequency of Dosing
1a	VIR-3434	300 mg	SC	12	Every 4 weeks
	TDF	300 mg ^b	Oral	\geq 308 ^c	Every day
2a	VIR-3434	Up to 300 mg ^a	SC	12	Every 4 weeks
	TDF	300 mg ^b	Oral	\geq 308 ^c	Every day
3a	VIR-3434	300 mg	SC	4-6 ^d	Every 8-12 weeks ^d
	TDF	300 mg ^b	Oral	\geq 252 ^c	Every day
4a	VIR-3434	300 mg	SC	12	Every 4 weeks
	VIR-2218	200 mg	SC	12	Every 4 weeks
	TDF	300 mg ^b	Oral	\geq 308 ^c	Every day
5a	VIR-3434	300 mg	SC	13	Every 4 weeks
	VIR-2218	200 mg	SC	13	Every 4 weeks
	PEG-IFN α	180 mcg	SC	48	Every week
	TDF	300 mg ^b	Oral	\geq 336 ^c	Every day

^a The dose of VIR-3434 will be determined before participants are enrolled in the cohort.

^b Tenofovir disoproxil fumarate dose (TDF) will be 300 mg as approved by the FDA. Supply outside the United States may be Tenofovir disoproxil (TD) 245 mg.

^c The minimum number of doses received by participant. Participants will continue receiving additional doses of TDF until they qualify for NRTI discontinuation.

^d The dosing regimen will be finalized before participants are enrolled in the cohort.

The total duration in the study for participants will be up to 100 weeks in cohorts 1a, 2a, and Cohort 4a, 92-96 weeks for Cohort 3a, and 104 weeks for Cohort 5a. This includes a Screening Period (up to 56 days or 8 weeks), Treatment Period (44 weeks for cohorts 1a and 2a, 36 or

40 weeks for Cohort 3a, 44 weeks for Cohort 4a, and 48 weeks for Cohort 5a) and a Follow-Up Period (up to 48 weeks) for all cohorts.

Once participants complete the Treatment Period per their respective cohort, they will enter the Follow-Up Period. Participants will discontinue the NRTI at the F1 or F12 visit in the Follow-Up Period if they meet the criteria to discontinue NRTI ([Section 1.2.4](#)) based on the data available. Additional study visits are required for participants who discontinue NRTI in the Follow-Up Period as indicated in the SOA in the study protocol. Participants who discontinue NRTI at F1 visit will be required to return to the site for additional visits at F2, F6, F10, F28, F32, F40, and F44. Participants who discontinue NRTI at F12 visit will be required to return to the site for additional visits at F14, F18, F22, F28, F32, F40, and F44.

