4. STATISTICAL ANALYSES

4.1. General Considerations

All analyses will use SAS version 9.4 or higher. The schedule of study assessments and time points are provided in the current PREVAIL master protocol and STRIVE sub-study.

Data will be provided in by-participant listings for the All Enrolled Set, unless otherwise specified.

Efficacy endpoints will be summarized by TDF/TD discontinued (participants who discontinued TDF/TD when the TDF/TD discontinuation criteria were met in the Follow-up period) and overall for each cohort.

Continuous variables will be summarized using the following descriptive summary statistics: the number of participants (n), mean, standard deviation (SD), median, Q1 (first quartile), Q3 (third quartile), minimum value (min), and maximum value (max), unless otherwise specified. In general, the precision of the measurement for each continuous variable will be used to determine the number of decimal places to present in tables, figures, and derived listings. Minimum and maximum values will be reported with the same precision as the units of measure. The mean and median will be reported to 1 additional decimal place, and the SD will be reported to 2 additional decimal places. Any values that require transformation to standard units (metric or SI) will be converted with the appropriate corresponding precision.

Categorical variables will be summarized using counts and percentages. Percentages will be rounded to one decimal place, except 100% will be displayed without any decimal places, and percentages will not be displayed for zero counts.

Baseline value: Unless otherwise specified, the baseline value will be defined as the most recent non-missing (scheduled or unscheduled) measurement collected prior to the initial administration of study intervention. If baseline cannot be determined due to missing data, no derivation will be performed, and baseline will be set to missing.

Change (absolute change) from baseline will be calculated as post-baseline value – baseline value.

Study day: The study day of an event/measurement is defined as the relative day of the event/measurement starting with the date of the first study drug administration (reference date) as Day 1 (there will be no Day 0).

The study day of event/measurement occurring before the first study drug administration will be calculated as:

$$\text{Study Day} = (\text{Date of event/measurement} - \text{Date of first study drug administration})$$

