- For efficacy response variables, the missing equals failure (MEF) approach will be used for the analysis, except for the sensitivity analysis for the primary endpoint described in [Section Error! Reference source not found.](#). The sensitivity analysis will be conducted to evaluate the impact of missing data, in which missing data will be imputed.
- Missing data will not be imputed, and will be considered as missing data that will not be included in the data summary statistics and analysis. Qualitative data will be imputed as follows:
 1. HBV DNA, for the analysis of the primary endpoint:

- a. If the missing data is reported as “Target Not Detected (TND)”, then the missing data point will be imputed as 0.
- b. If the missing data is reported as “< LLOQ”, then the missing data point will be imputed 1 unit less than the LLOQ value. That’s the LLOQ for HBV DNA is 20 IU/mL, so 19 IU/mL will be imputed.

2. HBs(e)Ag and Anti-HBs(e), for the analyses of primary and secondary efficacy endpoints:
If the missing data is reported as “Not Detected” or “Nonactive”, then the missing data point will be imputed as 0.
3. HBV RNA, for the analysis of an exploratory endpoint:
 - a. If the missing data is reported as “Not Detected”, then the missing data point will be imputed as 0.
 - b. If the missing data is reported as “< LLOQ”, then the missing data point will be imputed 1 unit less than the LLOQ value. That’s the LLOQ for HBV RNA is 0.49 log U/mL, so 0.48 log U/mL will be imputed.
 - c. If the missing data is reported as “> upper limit of quantification (ULOQ)”, then the missing data point will be imputed as 1 unit greater than the value of ULOQ. E.g., The ULOQ for HBV RNA is 6.0 log U/mL, so 6.1 log U/mL will be imputed.
 - d. If the missing data is reported as “Invalid” or “Quantity Not Sufficient (QNS)”, then the missing data will not be imputed and considered as missing data.
4. HBcrAg, for the analysis of an exploratory endpoint:
 - a. If the missing data is reported as “TND”, then the missing data point will be imputed as 0.
 - b. If the missing data is reported as “Target Detected (TD)”, then the missing data point will be imputed as 1 unit less than the LLOQ. That’s the LLOQ is $3.0 \log_{10} \text{U/mL}$, so $2.9 \log_{10} \text{U/mL}$ will be imputed.

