4.5. Exploratory Endpoints Analysis

4.5.1. Exploratory Efficacy Analysis

The analyses of the following exploratory efficacy endpoints will be conducted based on the FAS, unless otherwise specified. The numbering in the table below is consistent with the numbering of the endpoints in [Table 1](#). HBV RNA and HBcrAg values will be provided in a by-participant listing.

[figure not shown]
Exploratory Endpoints	Analysis Methods
1. Additional viral parameters associated with HBV and/or study intervention(s), including but not limited to HBV RNA and HBcrAg	
The observed values and the absolute change from baseline values at each visit up to End of Follow-up will be summarized using descriptive statistics (n, mean, SD, median, Q1, Q3, min, max) by cohort for the following HBV viral parameters:
 
 • HBV RNA in \log_{10} U/mL • HBcrAg in \log_{10} U/mL

Exploratory Endpoints	Analysis Methods
2. CCI	CCI
3. CCI	CCI
4. Emergence of viral resistance to study intervention(s)	Not covered by this SAP, will be analyzed separately.
7. For HBeAg-positive participants: time to achieve HBeAg loss (undetectable HBeAg) and/or anti-HBe seroconversion	Time to HBeAg loss and/or anti-HBe seroconversion will be summarized as a continuous variable. Participants with HBeAg loss with or without anti-HBe seroconversion will be listed.
8. Proportion of participants meeting criteria for NRTI discontinuation or retreatment in the study	The number and percentage of participants who meet NRTI discontinuation criteria NRTI retreatment criteria will be summarized by cohort. A by-participant listing will be provided for participants who met NRTI discontinuation criteria and retreatment criteria.
9. HBV DNA levels and change from baseline across timepoints in the study 10. Nadir and maximum change of HBV DNA level from baseline in the study	The observed values and the absolute change from baseline values of HBV DNA in both log IU/mL and IU/mL: a. at each visit b. at nadir up to EOS, will be summarized using descriptive statistics (n, mean, SD, median, Q1, Q3, min, max) by cohort. In addition, the change from baseline in \log_{10} IU/mL and absolute value in \log_{10} IU/mL at

Exploratory Endpoints	Analysis Methods
	each visit will be plotted for each participant by cohort.

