Section 9.4.1: TEAE definition for this sub-protocol: An AE that is reported with an onset date on or after the start of study intervention(s) until end of Follow-Up Period.	TEAE is defined as any AEs reported with an onset date on or after the first dose of study intervention(s) until the end of TE Period. The TE Period is defined as the time period on or from the start of study intervention(s) until the last dose of VIR-2218 + 30 days, or VIR-3434 + 24 weeks, or PEG-IFN α + 30 days, or TDF/TD + 30 days, whichever is later.
Protocol Section 9.5: Three interim analyses will be conducted for each cohort to evaluate the efficacy endpoints at Week 24, EOT, and 24 weeks post-EOT when all participants in the cohort completed the respective visits.	The Sponsor has decided to combine IA1 and IA2. As the study will be terminated earlier, the Sponsor also plans to merge IA3 with the final analysis.

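### Time to HBsAg loss and time to HBeAg loss are summarised as continuous variables without a censoring rule, so the mean and median describe only achievers and can shift with length of follow-up

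*SAP*

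**What the plan says.** The SAP covers STRIVE; the protocol supplied is for the sister sub-study THRIVE. This point concerns the STRIVE SAP.

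- **HBsAg.** For secondary endpoint 7, SAP 4.4.1 says "Time-to-HBsAg loss will be summarized as a continuous variable by cohort". The endpoint is also listed for Interim Analysis 1 (4.9.3.5.2) and Interim Analysis 2 (4.9.4.5.2).
- **HBeAg.** For exploratory endpoint 7, SAP 4.5.1 says "Time to HBeAg loss and/or anti-HBe seroconversion will be summarized as a continuous variable".
- **What a continuous summary contains.** SAP 4.1: "Continuous variables will be summarized using the following descriptive summary statistics: the number of participants (n), mean, standard deviation (SD), median", followed by quartiles, minimum and maximum.
- **Missing values.** SAP 4.1 does not impute them; they "will be considered as missing data that will not be included in the data summary statistics and analysis". The one rule that gives a value to an absent result is for a different type of variable: "For efficacy response variables, the missing equals failure (MEF) approach will be used for the analysis". It yields a non-response, not a time.
- **Length of observation.** SAP 1.2.3 gives total durations, including 8 weeks of screening, of up to 100 weeks for Cohorts 1a, 2a and 4a, and "92-96 weeks for Cohort 3a, and 104 weeks for Cohort 5a".
- **Early termination.** SAP 4.4.1 adapts secondary endpoints 9 and 11 for participants with "uncertain NRTI discontinuation status due to early study termination (e.g., no Follow-Up 12 visit"). SAP 4.10.1 also records that the study will end early and that the third interim analysis is merged with the final one.

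SAP 4.10.2 lists the time-to-event analyses among those changed in version 2.0. The current text still makes no provision for participants without the event.

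**The concern.** Time to nadir, in the same table cell as endpoint 7, exists for anyone with a post-baseline value, so a continuous summary suits it. Time to loss does not exist for a participant who never loses the antigen. With no censoring rule and no assigned value, that participant drops out of the mean, SD, median and quartiles.

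Two things follow. First, the figure answers a conditional question (how long did it take those who succeeded?) under an unconditional label. Second, longer observation admits later events, so the figure can rise with no change in drug effect. A reader comparing cohorts, or an interim with a final reading, could mistake observation time for speed of response.

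**Working it through.** **1. Is achievers-only the right reading?** The SAP does not say so in words. Its missing-data convention names withdrawal, loss to follow-up and intermittent gaps, not the absence of an event. But no time is defined for a non-event, values not available are left out of summary statistics, and missing-equals-failure supplies no time. The stated rules leave no other computable reading.

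**2. How many would contribute?** The plan gives no figure for these endpoints. The nearest is SAP Table 6. Its one-sided exact binomial power (null 2%, level 0.025) reproduces: 75.6% and 95.4% for n=10 (at least 2 responders needed), and 76.4% and 97.3% for n=15 (at least 3 needed), at true rates of 25% and 40%.

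Table 6 attaches no timepoint to those rates. Taking them, as an assumption, as the share who ever lose HBsAg:

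- Expected contributors, n × p: 10 × 0.25 = 2.5; 10 × 0.40 = 4; 15 × 0.25 = 3.75; 15 × 0.40 = 6.
- Chance of at most one contributor, so no SD, (1−p)^n + n·p·(1−p)^(n−1): 24.4% (n=10, 25%); 4.6% (n=10, 40%); 8.0% (n=15, 25%); 0.5% (n=15, 40%).

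The number of HBeAg-positive participants per cohort is not given, so the HBeAg endpoint cannot be sized.

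**3. How far could the figure move?** The documents give no event times, so two shapes are assumed, with time counted from first dose. Each event is assigned to the next visit: Weeks 1, 4, 8, and so on to end of treatment (EOT), then F1, F4, F8, F12, F16, F20, F24, F36 and F48 (SAP Tables 7 and 11). With visits t₁ < t₂ < … < T, t₀ = 0 and hazard λ, the achiever mean is

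Σ tⱼ·[exp(−λtⱼ₋₁) − exp(−λtⱼ)] / [1 − exp(−λT)].

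*(i) Losses continue through follow-up.* EOT is Week 44, total 44 + 48 = 92 weeks, λ = −ln(1−p)/92, that is 0.00313 per week (25%) or 0.00555 (40%).

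| Read to | 25% at Week 92 | 40% at Week 92 |
|---|---|---|
| EOT (Week 44) | 23.4 weeks | 23.0 weeks |
| Follow-Up 12 (Week 56) | 29.1 | 28.4 |
| Follow-Up 48 (Week 92) | 46.7 | 44.9 |

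The regimen is the same in each column; only the length of observation changes.

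*(ii) All losses occur on treatment.* λ = −ln(1−p)/44 and no events after EOT. Truncation after EOT then changes nothing. Treatment length still matters: one hazard read over 36 weeks gives 19.2 (25%) or 18.7 (40%) weeks, and over 48 weeks 24.7 or 23.7. Cumulative incidence at Week 36, 1 − exp(−36λ), is the same in both: 21.0% or 34.2%.

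**4. Does a censored estimate avoid this?** Under scenario (i), Kaplan-Meier cumulative incidence at a fixed week estimates the same quantity however long others are followed, provided censoring is unrelated to loss. Its precision is poor but similar to what is planned. For 4 of 15 with no censoring, the log-log interval is 10.9% to 56.4%, against an exact interval of 7.8% to 55.1%.

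**The case against.** The case for leaving this alone is substantial.

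- **Little rides on it.** SAP section 2 rules out hypothesis testing. Endpoint 7 is one of 16 secondary endpoints, the HBeAg version is exploratory, and no decision is tied to either.
- **The information is mostly there.** The summary prints n. HBsAg-loss proportions with Clopper-Pearson intervals, individual HBsAg plots, HBsAg listings, by-visit HBeAg proportions and a listing of participants with HBeAg loss are all planned. With 10 to 15 per cohort, a careful reader can recover individual times.
- **The shift is not established.** Scenario (i) puts only 12.9% (of 25%) or 21.7% (of 40%) before EOT. So 1 − 12.9/25 = about 49%, or 1 − 21.7/40 = about 46%, of losses fall after treatment. Nothing in the documents supports that, and scenario (ii) shows no effect of truncation after EOT.
- **Kaplan-Meier adds little where nobody is censored.** At EOT it then equals the proportion who ever lost the antigen. With no events, a log-log interval cannot be computed (chance 0.75^10 = 5.6% at n=10 and 25%).

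All of this stands as a limit on size and severity. It does not answer the labelling fault: the planned statistic is conditional on success and is not presented as such.

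**Conclusion.** The point holds as a fault in the stated method with limited harm. The change is worth making; the primary endpoint is untouched. That the summary covers achievers only is an inference, though a firm one. That it can shift with follow-up is certain in principle; the amount is not known. The range runs from no effect of truncation after EOT, if all losses are on treatment, to 23.4 against 46.7 weeks under a constant hazard reaching 25% at Week 92.

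Three stronger readings should be resisted.

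- A reader might infer that the 36- and 48-week figures show one STRIVE regimen yielding two answers. They do not. The 36-week schedule is Cohort 3a on its 12-weekly option and the 48-week schedule is Cohort 5a, and these receive different regimens. The figures show only what observation time alone would do.
- A reader might add that missing-equals-failure pulls the post-EOT proportions down after early termination, and offer that as evidence here. It concerns secondary endpoint 10, which is loss status at a visit. Time to first loss concerns ever having lost the antigen.
- A reader might extend the point to THRIVE. The THRIVE protocol takes secondary endpoints 1 to 8 from a Master Protocol that was not supplied, and it enrols only HBeAg-negative participants, so the HBeAg part has no counterpart there.

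**What to change.** In SAP 4.4.1 and 4.5.1:

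- Report Kaplan-Meier cumulative incidence of first HBsAg loss by cohort in the FAS, timed from first dose and censored at the last HBsAg assessment, with 95% confidence intervals at the cohort's planned EOT and at EOT + 24 weeks.
- Do the same for HBeAg loss in FAS participants who are HBeAg-positive at baseline, censored at the last HBeAg assessment.
- Leave anti-HBe seroconversion to the follow-up-visit proportions already planned, because post-baseline anti-HBe is read only in follow-up.
- State that the estimate is of ever having lost the antigen. It does not replace the by-visit proportions, which show current status and return.
- If the continuous summary is kept, label it 'among participants who achieved loss (n/N)'. This is the minimum change.

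The cost is a few lines of SAP text and one standard procedure on data already collected. The drawbacks are wide intervals, medians often not reached, and no log-log interval in a cohort without events.
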